5.0 Grouping Factors

5.1 Anatomical Sites of Tumor: Proximal lower extremity (includes knee) versus rest.

Note: As of July 19, 2023, there are no restrictions on number of patients enrolled per anatomical sites of tumor.

6.0 Registration Procedures

Patients will be registered by completing the registration through PTrax, and eligibility case report forms (CRFs) stored in MedidataRave.

- 6.1 Prior to patient enrollment, the investigator should ensure that all of the following requirements are met:
 - 6.1.1 The patient meets all inclusion criteria and exclusion criteria apply.
 - 6.1.2 The patient and investigator have signed and dated all applicable consent forms.
 - 6.1.3 All baseline assessments and examinations have been performed.
 - 6.1.4 All registration CRFs have been completed, signed, and dated.
 - 6.1.5 Protocol treatment must begin within 2 weeks of registration.

7.0 Protocol Treatment

7.1 Radiation Therapy

All patients enrolled on this trial will receive radiation therapy as detailed below.

7.1.1 Simulation

7.1.1.1 Patient Positioning and Immobilization

The patient may be treated in any appropriate, stable position. No specific immobilization is mandated. However, reproducible setup is critical and the use of standard immobilization devices for the extremity and/or truck is strongly encouraged.

Bolus should not be used unless:

- a. The tumor involves cutaneous structures,
- b. The tumor is very superficial such that adequate target dose (<90% prescription dose to the planning target volume (PTV)) cannot be delivered without it,
- c. Or, the surgeon indicates the biopsy scar and/or skin will not be resected.

7.1.1.2 Image Acquisition

Computed tomography (CT) imaging obtained during simulation will be the primary imaging modality for target delineation and

treatment planning. CT simulation imaging will be obtained per institutional policies and procedures.

Diagnostic or treatment position Magnetic Resonance Imaging (MRI) may be used to aid with target delineation and treatment planning at the discretion of the treating radiation oncologist. Similarly, use of intravenous contrast, breath hold techniques, and acquisition of 4D imaging sets are at the discretion of the treating radiation oncologist.

7.1.2 Target Volume Definitions

Treatment planning will be based on the following definitions.

7.1.2.1 GTV

Gross tumor volume (GTV) is the volume of all known disease based on CT simulation imaging and physical exam. If MRI is used for target delineation, GTV is best delineated on T1 contrast sequences.

If there has been prior surgical violation of the sarcoma (for example, a non-oncologic partial or positive-margin excision), the GTV may be extended to include the initial region of gross tumor as well as any disturbed tissues. In most cases, an open biopsy scar should not be included in the GTV as standard of care is for the incision to be resected. In the unusual situation where an open biopsy scar will not be resected, this should be confirmed with the surgeon and included in the GTV.

7.1.2.2 CTV

Clinical target volume (CTV) includes the GTV and sites of potential occult tumor involvement. A 2.0-4.0 cm longitudinal and 1.0-1.5 cm radial expansion from GTV will be used to generate the CTV. The expansions should follow natural planes of spread for sarcomas, while respecting intact bone and compartment boundaries. If MRI is used for target delineation, the CTV should also include physician-determined suspicious peri-tumoral edema seen on T2 sequence images. In patients who received neoadjuvant chemotherapy and experienced a reduction in tumor volume with chemotherapy, the pre-chemotherapy extent of the tumor in soft tissues should be included in the CTV.

7.1.2.3 PTV

A geometric margin of 5-10 mm will be used to create PTV. Daily image guidance is required.

7.1.2.4 Proton Therapy

- 7.1.2.4.1 GTV is the same for protons and photons
- 7.1.2.4.2 CTV is the same for protons and photons
- 7.1.2.4.3 PTV is not the same as photons due to differences in beam penetration with movement and set up uncertainty. PTV varies with each individual field and requires additional adjustments based on set up error for the involved body site. In general, adjustment margins are usually 2-7 mm and will follow institutional policies and procedures.

7.1.3 Organs at Risk Contouring Definitions

Only organs at risk relevant to the treatment field within 2 cm superior and inferior to the PTV edge should be contoured.

7.1.3.1 Bone avoid (only applicable for extremity tumors)

The bone immediately adjacent to the gross tumor is contoured as bone avoid. The bone avoid structure will extend 2 cm superior and inferior to the PTV edge.

7.1.3.2 Soft tissue avoid (only applicable for extremity tumors)

The soft tissue surrounding the PTV and extending 2 cm superior and inferior to the PTV edge is defined as soft tissue avoid. To create the soft tissue avoid structure, an intermediate structure is first created defined as PTV + a 2.0 cm geometric expansion.

Then, the body only contour is subtracted from the PTV+2.0 cm intermediate structure and limited to 2 cm superior and inferior to the PTV edge. This final soft tissue avoid structure is cropped out of bone avoid and volumes $<1\text{cm}^3$ are erased (Figure 1).

Figure 1. Example of the soft tissue avoid structure in axial plane. PTV is in magenta, soft tissue avoid is in light green, and bone avoid is in orange.

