7.1.4.4.2 Major Deviation Definition

- a) PTV_4275 D95% $<90\%$
AND / OR
- b) $>25\%$ of PTV_4275 receives $\geq 110\%$ of prescription dose
AND / OR
- c) Dose to the priority 1 organs at risk is more than the recommended limit (Table 2.0)

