7.1.4.5 Organs at Risk Dose Constraints

Normal tissue dose constraints are listed in Table 2.0. Every effort should be made to avoid treating the full circumference of any extremity. There is no special requirement for skin dose limit. However, full prescription dose to skin over areas commonly traumatized (e.g., elbow, knee, shin) should be avoided unless in the PTV.

While every effort should be made to deliver prescription doses to the PTV as specified while adhering to normal tissue constraints, it is recognized that certain anatomical factors may prevent this. As such, if normal tissue constraints are unachievable, the patient will be taken off the trial and treated with standard pre-operative RT to 50 Gy in 25 fractions meeting standardly accepted constraints for that fractionation schedule.

Table 2.0 –Organs at Risk Dose Constraints

Organ at Risk	Dose Constraints	Priority
Bone avoid	Mean < 32 Gy V35Gy < 64% V35Gy < 40%	1 1 2
Soft tissue avoid	Mean < 26 Gy V18Gy < 50%	2 1
Joint (only major joints: hip/knee/shoulder)	V42.56Gy < 50%	2
Anus	Max V42.75Gy (%) V40.6Gy (%)	Report Report Report
Genitalia	Max Mean < 26 Gy	Report 1

Testis (if fertility preservation desired)	V1Gy \leq 60% V1Gy \leq 50%	1 2
Ovaries (if fertility preservation desired)	V4.8Gy \leq 60% V1Gy \leq 50%	1 2
Lungs	V18Gy \leq 20%	1
Brachial plexus	Max $<$ 48 Gy	1
Heart	Mean $<$ 10 Gy	1
Esophagus	Mean $<$ 26 Gy	1
Liver	Mean $<$ 26 Gy	1
Stomach	Max \leq 38 Gy	1
Small Bowel	Max \leq 45 Gy; if in PTV V42.75Gy $<$ 20 cc V26.5Gy $<$ 100 cc V39Gy $<$ 60 cc	21 2 1
Large Bowel	Max $<$ 45 Gy; if in PTV V42.75Gy (%) V40.6Gy (%) V42.75Gy (cc) $<$ 50 cc	2Report Report 2
Kidney	V11.8 Gy $<$ 10% for total kidney volume V11.8Gy $<$ 33% for each kidney V5Gy for each kidney	1 2 Report
Spinal Cord	Max	Report

	V39Gy <0.1%	2
Bladder	Max	Report
	V42.75Gy <50%	2
	V30Gy <60%	2

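### Protocol 7.1.3.2 (extremity tumours only): the written step for building soft tissue avoid yields none of the tissue the section defines; its operands appear reversed

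*Combined protocol and SAP*

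**What the plan says.** Section 7.1.3.2 applies to extremity tumours only. It opens with a definition: "The soft tissue surrounding the PTV and extending 2 cm superior and inferior to the PTV edge is defined as soft tissue avoid". It then gives a recipe. The PTV is expanded geometrically by 2.0 cm to form an intermediate structure, and "the body only contour is subtracted from the PTV+2.0 cm intermediate structure". The result is limited to 2 cm above and below the PTV edge, cropped out of bone avoid, and cleared of volumes under 1 cm³. Figure 1 is captioned "Example of the soft tissue avoid structure in axial plane".

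The 2 cm longitudinal limit is not special to this structure. Section 7.1.3 says "Only organs at risk relevant to the treatment field within 2 cm superior and inferior to the PTV edge should be contoured", and 7.1.3.1 says "The bone avoid structure will extend 2 cm superior and inferior to the PTV edge".

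Table 2.0 in 7.1.4.5 gives the structure two limits, "Mean < 26 Gy V18Gy < 50"%. The mean is priority 2 and V18Gy is priority 1. Section 7.1.4.4.2 makes it a major deviation when "Dose to the priority 1 organs at risk is more than the recommended limit". Section 7.1.4.5 adds that "if normal tissue constraints are unachievable, the patient will be taken off the trial".

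**The concern.** To subtract A from B is to keep the part of B that is not in A. Read that way, the recipe removes the patient from the expanded PTV, when its purpose is to isolate tissue in the patient around the PTV. The recipe therefore contradicts the definition two sentences above it.

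The structure carries a priority 1 limit. Whether a plan meets that limit bears on the major-deviation label and on whether the patient continues on the trial schedule or is treated with 50 Gy in 25 fractions. A structure with those consequences should be reproducible from the written text. If the sentence has to be repaired in the reader's head, more than one repair is available, and the repairs are different structures.

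**Working it through.** The plan states no numerical result for this step, so there is no figure to reproduce. The check is set algebra.

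**Notation.** B = body; P = PTV, taken as lying within the body; E = PTV+2.0 cm, which contains P. Any soft tissue surrounding the PTV lies in B \ P. All inputs come from 7.1.3.2.

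**Reading 1: *body only contour* means the body.** The step is E \ B. Its intersection with B is empty, so the result is either nothing or space outside the skin.

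**Reading 2: *body only* means body minus PTV.** The step is E \ (B \ P) = (E \ B) ∪ P. This has volume in the patient, but that volume is the PTV itself. Its intersection with B \ P is empty, so it again holds no surrounding soft tissue.

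**Later steps.** The longitudinal limit, the bone-avoid crop and the erasure of small volumes each produce a subset of what went in. None can restore tissue. No other section restates or corrects the step.

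**Candidate repairs.**
- (a) Operands swapped: B \ E, limited to 2 cm superior and inferior. This changes only the order of two terms. It needs the longitudinal limit, because B \ E would otherwise run the length of the scanned limb.
- (b) A 2 cm ring: (E ∩ B) \ P. This also fits the definition. It needs a PTV subtraction that the text never mentions. The longitudinal limit is redundant, because a 2.0 cm expansion already ends there.

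The longitudinal clause therefore leans towards (a). It does not settle the matter, because the same limit is stated for organs at risk generally in 7.1.3 and for bone avoid in 7.1.3.1.

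**Do the repairs differ?** (a) lies wholly outside E and (b) wholly inside it, so they share no volume. The 18 Gy level is 18/42.75 = 42.1% of the prescription. Suppose, hypothetically, that the 18 Gy isodose coincided with the surface of E. Then V18Gy would be 100% for (b) and 0% for (a). This shows only that the two can disagree on V18Gy < 50%, not how often they would.

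**Numerical check of the algebra.** The assumptions are 2 mm voxels, a cylindrical limb, a cylindrical PTV 12 cm long, and a central bone of 1.4 cm radius removed from (a) and (b). Lengths are in cm and volumes in cm³.

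| Limb radius / PTV offset / PTV radius | Reading 1: total (in body) | Reading 2: in body (of which outside PTV) | (a) | (b) | Overlap of (a) and (b) |
|---|---|---|---|---|---|
| 9 / 5 / 3.5 | 154 (0) | 467 (0) | 2793 | 764 | 0 |
| 9 / 3 / 3.5 | 0 (0) | 467 (0) | 2672 | 934 | 0 |
| 6 / 3 / 2.5 | 144 (0) | 235 (0) | 1019 | 494 | 0 |
| 11 / 2 / 5 | 0 (0) | 937 (0) | 3791 | 1385 | 0 |

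The zeros follow from the algebra and hold for any anatomy. The volumes depend on the assumed shapes and are not evidence about this trial.

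**The case against.** The strongest reply is that this is an editorial slip. The opening sentence of 7.1.3.2 gives the governing definition, no planner would contour air after reading it, and the recipe ends by pointing to Figure 1, which shows the finished structure against the PTV and bone avoid. That image is missing only from the copy reviewed, so its absence is not a fault of the plan. Section 7.1.8 also requires a co-chair to approve all target volumes and final plans.

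Most of this stands, and it is why the effect is small. It does not make the sentence right: a correct figure beside a contradictory instruction still leaves the instruction to be corrected.

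The reply also has force on ambiguity. The text favours the swapped operands over the ring, because the swap is the smaller edit and gives the longitudinal limit a purpose. It does not prove that choice.

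Some stronger inferences are tempting and should be resisted:
- A reader might say that the literal structure always has zero volume in the patient. Under Reading 2 it contains the PTV, so the safe statement is that it contains none of the surrounding soft tissue.
- A reader might infer that extremity plans were contoured inconsistently, that deviation flags are unreliable, or that stored contours need re-checking. Nothing in the documents shows inconsistent contouring.
- A reader might want a distance from the PTV at which the two repairs diverge on V18Gy. That would require assumed limb shapes and dose fall-off that the documents do not supply.

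**Conclusion.** The written construction step in 7.1.3.2 is wrong: on either reading of *body only* it gives none of the tissue the section defines, and nothing later repairs it. This rests on the ordinary meaning of subtraction and on the PTV lying within the body, not on any assumed anatomy. The operands appear reversed, but which structure is intended is for Figure 1 and the radiation oncology team to settle.

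The point is minor. It concerns extremity tumours only, and planners are probably guided correctly already. It matters to the extent that a priority 1 limit, and the major-deviation and off-trial rules tied to it, should rest on a structure that can be rebuilt from the text. It does not touch the sample size, significance level, power or primary estimate, and patients with a major deviation stay in the primary analysis under 13.4.

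**What to change.** Replace the subtraction sentence in 7.1.3.2 with the one explicit operation that Figure 1 shows. Either:

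- (a) body minus (PTV+2.0 cm), limited to 2 cm superior and inferior to the PTV edge; or
- (b) (PTV+2.0 cm) intersected with body, minus PTV.

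In both cases, follow it with the existing crop out of bone avoid and the erasure of volumes under 1 cm³. The radiation oncology team makes the choice.

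The cost is a one-sentence protocol clarification. Treatment, sample size and analysis do not change.

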7.1.4 Radiation Therapy Planning

7.1.4.1 Dose definition

Photon dose will be specified in centigray (cGy). For proton therapy, the absorbed dose is specified in centigray equivalents (CGE), which is the same as ICRU 78 D_{RBE} using a standard RBE of 1.10 with respect to water.

7.1.4.2 Target Dose

The radiation dose prescribed to the PTV will be 4275 cGy in 15 daily fractions over 3 weeks. Treatment will be delivered once daily, except on weekends and holidays. Twice daily (BID) treatments are not allowed.

7.1.4.3 Treatment Planning

The treatment technique and modality are at the discretion of the treating radiation oncologist. The patient may be treated using conventional 3D radiotherapy (3DCRT); Intensity Modulated Radiotherapy (IMRT), rotational IMRT techniques such as Volumetric Arc Radiation Therapy (VMAT), or proton therapy (3D or Intensity Modulated Proton Therapy (IMPT)).

The dose will be prescribed to the treatment isocenter, which serves as the ICRU reference point. Appropriate beam modality and energy should be selected for the size and depth of the tumor, tissue, and site to be treated. Every attempt should be made to use techniques (i.e., 3DRT, IMRT, VMAT, etc.) and modalities (i.e.,

electrons, photons, protons) which avoid unnecessary irradiation of critical normal tissues.

7.1.4.4 Target Dose Requirements and Uniformity

Table 1.0 lists dose volume histogram (DVH) requirements for CTV and PTV. If DVH requirements cannot be met, an explanation must be submitted to the study co-chairs ([name], M.D. or [name], M.D.).

Table 1.0 – DVH requirements for CTV and PTV

Structure	DVH Endpoint	Requirement	Priority	DVH Endpoint	Requirement	Priority
CTV_4275	D95%[%]	$\geq 100\%$	2	D95%[%]	$\geq 95\%$	1
				CV95%[cc]	$<0.5\text{cc}$	1
	V110%		Report			
PTV_4275	D95%[%]	$\geq 99\%$	2	D95%[%]	$\geq 95\%$	1
				CV95%[cc]	$<0.5\text{ cc}$	1
	V110%		Report			

7.1.4.4.1 Minor Deviation Definition

- a) PTV_4275 D95% $<95\%$ but $\geq 90\%$
AND / OR
- b) $>20\%$ but $\leq 25\%$ of PTV_4275 receives $\geq 110\%$ of prescription dose

7.1.4.4.2 Major Deviation Definition

- a) PTV_4275 D95% $<90\%$
AND / OR
- b) $>25\%$ of PTV_4275 receives $\geq 110\%$ of prescription dose
AND / OR
- c) Dose to the priority 1 organs at risk is more than the recommended limit (Table 2.0)

7.1.4.5 Organs at Risk Dose Constraints

Normal tissue dose constraints are listed in Table 2.0. Every effort should be made to avoid treating the full circumference of any extremity. There is no special requirement for skin dose limit. However, full prescription dose to skin over areas commonly traumatized (e.g., elbow, knee, shin) should be avoided unless in the PTV.

While every effort should be made to deliver prescription doses to the PTV as specified while adhering to normal tissue constraints, it is recognized that certain anatomical factors may prevent this. As such, if normal tissue constraints are unachievable, the patient will be taken off the trial and treated with standard pre-operative RT to 50 Gy in 25 fractions meeting standardly accepted constraints for that fractionation schedule.

Table 2.0 –Organs at Risk Dose Constraints

Organ at Risk	Dose Constraints	Priority
Bone avoid	Mean < 32 Gy V35Gy < 64% V35Gy < 40%	1 1 2
Soft tissue avoid	Mean < 26 Gy V18Gy < 50%	2 1
Joint (only major joints: hip/knee/shoulder)	V42.56Gy < 50%	2
Anus	Max V42.75Gy (%) V40.6Gy (%)	Report Report Report
Genitalia	Max Mean < 26 Gy	Report 1

Testis (if fertility preservation desired)	V1Gy \leq 60% V1Gy \leq 50%	1 2
Ovaries (if fertility preservation desired)	V4.8Gy \leq 60% V1Gy \leq 50%	1 2
Lungs	V18Gy \leq 20%	1
Brachial plexus	Max $<$ 48 Gy	1
Heart	Mean $<$ 10 Gy	1
Esophagus	Mean $<$ 26 Gy	1
Liver	Mean $<$ 26 Gy	1
Stomach	Max \leq 38 Gy	1
Small Bowel	Max \leq 45 Gy; if in PTV V42.75Gy $<$ 20 cc V26.5Gy $<$ 100 cc V39Gy $<$ 60 cc	21 2 1
Large Bowel	Max $<$ 45 Gy; if in PTV V42.75Gy (%) V40.6Gy (%) V42.75Gy (cc) $<$ 50 cc	2Report Report 2
Kidney	V11.8 Gy $<$ 10% for total kidney volume V11.8Gy $<$ 33% for each kidney V5Gy for each kidney	1 2 Report
Spinal Cord	Max	Report

	V39Gy <0.1%	2
Bladder	Max	Report
	V42.75Gy <50%	2
	V30Gy <60%	2

7.1.5 Radiation Therapy Delivery

Radiation therapy will be delivered using a linear accelerator or proton gantry. Patients will be set up according to the instructions from CT simulation and treatment planning. Image guidance procedures will be determined at the discretion of the treating radiation oncologist.

7.1.6 Treatment Delays

There will be no planned rests or breaks from treatment. Once radiation therapy has been initiated, treatment will not be interrupted except for severe illness or unplanned emergencies. The reason for any interruptions greater than three days should be recorded and submitted to the study Chair ([name], M.D.). When treatment interruptions or delays occur, the total number of fractions or cumulative dose should not be modified.

7.1.7 Special Considerations

7.1.7.1 Tumor motion

Acquisition of 4D imaging sets, use of breath hold techniques, or treatment delivery via phase gating for tumors with internal motion are at the discretion of the treating radiation oncologist. In these cases, an internal target volume (ITV) will be delineated per standard institutional policies and procedures.

7.1.7.2 Nodal Radiation

For tumors with no evidence of nodal involvement, the draining regional lymph nodes should not be irradiated. Tumors with nodal involvement are excluded on this trial.

7.1.8 Quality Assurance

All target volumes and final treatment plans must be submitted for review and approval by a study co-chair ([name], M.D. or [name], M.D.).

7.1.9 Intraoperative and Postoperative Radiation Therapy

Use of intraoperative and postoperative radiation therapy is discouraged. If intraoperative or postoperative radiation therapy is deemed to be of benefit for a high-risk case, contact a study co-chair ([name], M.D. or [name], M.D.).

7.2 Surgery

Patients will undergo oncologic resection ideally 3-4 weeks after completion of preoperative radiation therapy per institutional standards. If surgery is not feasible during this ideal period, it must be performed within 6 weeks (\pm 1 week) of completing preoperative radiation therapy. Acute wound complications will be recorded as detailed in section 11.1.

7.3 Chemotherapy

The use of chemotherapy will be at the discretion of the multidisciplinary team and medical oncology consultant involved in the case. Chemotherapy will not be used concurrently with radiation therapy on this study. In cases where chemotherapy is used either neo-adjuvantly or adjuvantly, the agents used and number of cycles/doses of chemotherapy will be documented.

7.4 Patient reported questionnaires

All patients will complete Patient-Reported Outcomes Measurement Information System (PROMIS) and Toronto Extremity Salvage Score (TESS) questionnaires at baseline, post-radiotherapy, and post-surgery time-points as detailed in section 4.0.

8.0 Dosage Modifications Based on Adverse Events

N/A

9.0 Ancillary Treatment/Supportive Care**9.1 Permitted Supportive Therapy**

All supportive therapies for optimal medical care are allowed during the study period at the discretion of the provider within the parameters of the protocol. Examples include skin care, physical therapy and rehabilitation, occupational therapy, anti-emetics, anti-diarrheals, prophylaxis for constipation, anti-inflammatories, anti-pyretics, intravenous fluids, and appetite enhancers.

9.2 Non-permitted Supportive Therapy

No investigational agents are permitted.

10.0 Adverse Event (AE) Monitoring and Reporting

10.1 Definitions

Adverse Event- An untoward or undesirable experience associated with the use of a medical product (i.e. drug, device, biologic) in a patient or research subject.

Serious Adverse Event – Any grade 4 or 5 adverse event as defined by CTCAE v5.0. Adverse events are classified as serious or non-serious. Serious problems/events can be well defined and include in general:

- Death
- Life threatening adverse experience where emergent lifesaving treatment is necessary.

Unanticipated Problems Involving Risks to Subjects or Others (UPIRTSO)- Any unanticipated problem or adverse event that meets the following three criteria:

Serious: Serious problems or events that results in significant harm, (which may be physical, psychological, financial, social, economic, or legal) or increased risk for the subject or others (including individuals who are not research subjects). These include: (1) death; (2) life threatening adverse experience; (3) hospitalization - inpatient, new, or prolonged; (4) disability/incapacity - persistent or significant; (5) birth defect/anomaly; (6) breach of confidentiality and (7) other problems, events, or new information (i.e. publications, DSMB reports, interim findings, product labeling change) that in the opinion of the local investigator may adversely affect the rights, safety, or welfare of the subjects or others, or substantially compromise the research data,

AND

Unanticipated: (i.e. unexpected) problems or events are those that are not already described as potential risks in the protocol, consent document, not listed in the Investigator's Brochure, or not part of an underlying disease. A problem or event is "unanticipated" when it was unforeseeable at the time of its occurrence. A problem or event is "unanticipated" when it occurs at an increased frequency or at an increased severity than expected,

AND

Related: A problem or event is "related" if it is possibly related to the research procedures.

Preexisting Condition- A preexisting condition is one that is present at the start of the study. A preexisting condition should be recorded as an adverse event if the frequency, intensity, or the character of the condition worsens during the study period. At screening, any clinically significant abnormality should be recorded as a preexisting condition. At the end of the study, any new clinically significant findings/abnormalities that meet the definition of an adverse event must also be recorded and documented as an adverse event.

